| 
 b. No ongoing requirement for dexamethasone as therapy for CNS disease; anticonvulsants at a stable dose are allowed. c. Completed stereotactic radiosurgery at least 1 week prior to Cycle 1, Day 1 or whole-brain radiation at least 2 weeks prior to Cycle 1, Day 1. - History of leptomeningeal carcinomatosis - Prior palliative radiotherapy outside the CNS within 2 weeks of the first dose of study drug - Treatment with systemic immunosuppressive medications (including but not limited to, dexamethasone at doses > 2 mg daily (or equivalent dose of other corticosteroids), cyclophosphamide, tacrolimus, sirolimus, azathioprine, methotrexate, thalidomide, and antitumor necrosis factor [anti-TNF] agents) within 2 weeks prior to initiating trial therapy (Inhaled or topically applied steroids, and acute and chronic standard-dose NSAIDs are permitted. Replacement steroids are also permitted). |
| 
Intervention and Mode of Delivery:
 
Nivolumab 3 mg/kg IV every 2 weeks and Ipilimumab 1 mg/kg IV every 6 weeks
 |
| 
Duration of Intervention and Evaluation:
 
Combination therapy with ipilimumab and nivolumab will be continued until disease progression or unacceptable toxicity. Patients with progression of disease by RECIST v1.1 without decline in performance status will be allowed to continue trial therapy if their treating physician believes they are deriving clinical benefit from study therapy.
 
Both RECIST v1.1 and immune-related response criteria (irRC) will be used to assess response to therapy. All patients who receive at least one dose each of ipilimumab and nivolumab will be considered evaluable.
 
Tumor response will be based on tumor assessments at screening, every 9 weeks from the first dose (for the first 24 weeks) and thereafter every 12 weeks until investigator-assessed initial disease progression.
 |

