8. CRITERIA FOR RESPONSE

Anti-tumor activity: data on objective response, progression free survival, and duration of response will be listed for all patients in the study and summarized overall.

Objective response is defined as a complete or partial response, as determined by investigator assessment using RECIST v1.1 and irRC (see appendix 3 and 4) and confirmed by repeat assessments ≥ 4 weeks after initial documentation. Patients not meeting these criteria, including patients without any post baseline tumor assessment, will be considered non-responders in the analysis of objective response.

Duration of objective response will be analyzed for the subset of patients who achieved an objective response. Duration of response is defined as the time from the initial complete or partial response to the time of disease progression or death, whichever occurs first. If a patient does not experience death or disease progression before the end of the study, duration of response will be censored at the day of the last tumor assessment. If no tumor assessments were performed after the date of the first occurrence of a complete or partial response, duration of objective response will be censored at the date of the first occurrence of a complete or partial response plus 1 day.

Progression-free survival is defined as the time from the first day of nivolumab treatment until progression of disease using RECIST v1.1 and irRC (see appendix 3 and 4). If a patient has not experienced progressive disease or death, PFS will be censored at the day of the last tumor assessment. Patients with no post baseline tumor assessments will be censored at the date of first study treatment plus 1 day.

[figure not shown]
Overall survival is defined as the time from the first day of treatment until death from any cause. If a patient has not experienced death, OS will be censored at the day of last follow-up.

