9. STATISTICAL CONSIDERATIONS

This trial is designed to determine the objective response rate (ORR) using RECIST v1.1 and irRC to nivolumab and ipilimumab when administered in combination to patients with advanced NSCLC and primary resistance to PD-1 axis inhibitor therapy. Details on the response criteria and its duration are described in Section 8 of this protocol. For our primary endpoint we will employ a Simon two-stage design. This design is based on our intuition for a very low response rate and not on any specific experimental evidence. The study design will terminate early if there are no responses or prolonged stability (≥ 24 weeks) using irRC among the first 10 patients enrolled. Otherwise we will enroll a maximum of 40 and reject the null hypothesis if we observe 4 or more

positive responses. For a null hypothesis with a 5% ORR and alternative with a 19% ORR, this criterion has significance level 0.1 and power greater than 85%. The null and alternative hypothesis rates are not motivated by experimental evidence but rather, are examples of one pair of hypotheses that can be tested using this design.

An operating characteristic of this design with other ORRs is plotted here:

We anticipate enrollment at a rate of at least 2 patients per month. Patients who drop out or leave the study before receiving any experimental treatment will be replaced. Patients who leave the study after receiving any study treatment will be considered as treatment failures and not be replaced.

Our secondary analyses correlate ORR, time-to-event measures and correlative metrics listed in Section 7. Specifically, duration of response, progression-free survival (PFS) and overall survival (OS) will be estimated along with the corresponding 95% CI, plotted using the Kaplan-Meier method. These plots will also be prepared separately by RECIST v 1.1 criteria and irRC and tested using the log-rank test. Duration of response, OS, and PFS are defined in Section 8.

Marker data and other metrics listed in Section 7 will be correlated to ORR and PFS using Cox proportional hazard regression methods. These values will be analyzed marginally using heatmaps and single linkage to identify any subpopulations.

The following analysis sets will be defined in this trial:

- Full Analysis Set: All subjects who receive at least 1 dose of any trial treatment.

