Step 5. Calculate the change in tumor burden relative to baseline and the change in tumor burden relative to nadir.

Step 6. Derive the overall response using the table below.

| Overall Response | Criterion |
|------------------|---|
| irCR | Complete disappearance of all lesions (whether measurable or not, and no new lesions) confirmed by a repeat, consecutive assessment ≥ 4 weeks from the date first documented |
| irPR | Decrease in tumor burden $\geq 50\%$ relative to baseline confirmed by a consecutive assessment ≥ 4 weeks from the date first documented |
| irSD | Criteria for irCR, irPR, and irPD are not met; does not require confirmation |
| irPD | Increase in tumor burden $\geq 25\%$ relative to nadir confirmed by a consecutive assessment ≥ 4 weeks from the date first documented |

irCR = immune-related complete response; irPD = immune-related progressive disease; irPR = immune-related partial response; irSD = immune-related stable disease.

DETERMINATION OF irBOR

Once a patient has completed all tumor assessments, his/her irBOR may be determined:

| Condition | irBOR |
|---|-------|
| At least one irCR | irCR |
| At least one irPR and no irCR | irPR |
| At least one irSD and no irCR and no irPR | irSD |
| At least one irPD and no irCR, no irPR, and no irSD | irPD |

irBOR = immune-related best overall response; irCR = immune-related complete response; irPD = immune-related progressive disease; irPR = immune-related partial response; irSD = immune-related stable disease.

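### Section 9's log-rank test between RECIST v1.1 and irRC curves treats the same patients as independent groups; its groups are not stated and neither possible reading is sound for all three endpoints

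*Combined protocol and SAP*

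**What the plan says.** Section 9 first lists the time-to-event outputs: "duration of response, progression-free survival (PFS) and overall survival (OS) will be estimated along with the corresponding 95% CI, plotted using the Kaplan-Meier method". The next sentence is the one at issue: "These plots will also be prepared separately by RECIST v 1.1 criteria and irRC and tested using the log-rank test". It gives no null hypothesis, no significance level and no paired, stratified or clustered form of the test. The only split it names is the pair of response criteria. The synopsis, under Statistical Methods, has the Kaplan-Meier plots and Cox models but no log-rank test.

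The synopsis (Duration of Intervention and Evaluation) applies both criteria in the trial: "Both RECIST v1.1 and immune-related response criteria (irRC) will be used to assess response to therapy". Section 8 defines PFS once, from a single start day, with two progression rules: "Progression-free survival is defined as the time from the first day of nivolumab treatment until progression of disease using RECIST v1.1 and irRC". OS involves neither rule: "Overall survival is defined as the time from the first day of treatment until death from any cause". Duration of response is confined to responders: "Duration of objective response will be analyzed for the subset of patients who achieved an objective response".

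**The concern.** The ordinary two-sample log-rank variance assumes that the two groups hold different, independent patients. If the groups are the RECIST reading and the irRC reading, each patient enters the PFS analysis twice, usually with equal or close dates. The variance is then overstated and the test rejects too rarely.

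What is at stake is interpretation. Appendix 4 brings in irRC because conventional criteria may not capture the activity of immunotherapy. A large p-value from a test that can hardly reject would look like evidence that the choice of criterion makes no difference, even if a fair share of patients had different progression dates.

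**Working it through.** **No figure to reproduce.** The documents attach no alpha, power or event count to this test, so the check is of its behaviour under each reading.

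**Reading 1: RECIST curve against irRC curve**

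*OS.* Time and event indicator are the same under both labels. At every death time observed equals expected in each group, so z = 0 and p = 1 whatever the data.

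*PFS, equal curves.* Input from the documents: at most 40 patients in the primary cohort (Section 9). Assumptions, not from the documents: exponential times with median 4 months, censoring uniform over 6 to 24 months, Gaussian copula between the two times, two-sided nominal 5%, 3,000 runs per setting.

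| Within-patient correlation | SD of z | True size at nominal 5% |
|---|---|---|
| 0 | 1.00 | 4.9% |
| 0.3 | 0.88 | 2.7% |
| 0.5 | 0.76 | 1.1% |
| 0.7 | 0.63 | 0.2% |
| 0.9 | 0.40 | 0.0% |

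The mechanism is visible in the SD of z, which should be 1. At correlation 0.5 the cut-off of 1.96 lies 1.96 / 0.76 = 2.6 true standard deviations out; at 0.9 it lies 1.96 / 0.40 = 4.9 out. A second run under other assumptions (median PFS 10 weeks; scans at weeks 9, 18, 30 and every 12 weeks; 1,500 runs) gave 1.3% at correlation 0.5 and 0.07% at 0.8. Its size at zero correlation was 6.7%, so the pattern matters more than the decimals.

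*PFS, real differences.* Let a fraction of patients have later irRC progression and the rest identical dates (1,000 runs each; same median and censoring as the table).

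| Fraction later | Delay (months) | Log-rank rejects | Median p |
|---|---|---|---|
| 10% | 1.0 | 0.0% | 0.93 |
| 20% | 2.1 | 0.0% | 0.71 |
| 30% | 4.0 | 0.3% | 0.34 |
| 50% | 4.0 | 20.7% | 0.11 |

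*Duration of response.* RECIST and irRC responders come from one cohort, but the sets can differ, so the data are partly paired. They are also few: 40 × 0.05 = 2 expected responders at the null rate and 40 × 0.19 = 7.6 at the alternative.

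**Reading 2: responders against non-responders, once per criterion**

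*Duration of response.* Non-responders have none, so there is no second group.

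*PFS and OS.* Section 8 requires confirmation at least 4 weeks after first documentation, and the first scheduled scan is at about week 9. A patient on schedule must therefore stay alive and progression-free to about week 9 + 4 = 13 to count as a responder, whereas anyone failing sooner is a non-responder by definition. Responders carry guaranteed time, and Section 9 has no landmark or time-dependent handling.

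**Direction of the PFS difference**

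Appendix 3 counts a new lesion as progression, while Appendix 4 adds measurable new lesions to the tumor burden and requires a 25% rise "relative to nadir confirmed by a consecutive assessment". Both features tend to delay irRC progression. But the irRC burden is a sum of products of two diameters, so a 25% rise is √1.25 = 1.118, about 12% per diameter under uniform growth. RECIST needs 20% in summed diameters plus 5 mm, and 20% in both diameters is 1.2² = 1.44, or 44% in product. From growth of index lesions alone, irRC can trigger first. Appendix 4 also does not say whether irPD is dated at first documentation or at confirmation.

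**The case against.** The strongest reply is that the sentence never names its groups. The same paragraph opens by relating response to time-to-event measures, and drawing OS separately by criterion makes sense only if the criterion defines response groups. Responders and non-responders are distinct patients, so pairing would not arise. The ambiguity stands, and it is why the fix begins by asking for the groups. It does not rescue the sentence: this reading fails for duration of response and brings guarantee-time bias for PFS and OS, and the synopsis already assigns the relation of OS and PFS to response to Cox regression.

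Several stronger conclusions are tempting, and the documents do not support them:

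- A reader might infer that the PFS p-value has no meaning. Under positive correlation it errs in a known, conservative direction.
- A reader might infer that irRC progression can only come later, so that non-significance is almost certain. The thresholds above allow the reverse order, and a 4-month delay in half of patients gave 20.7% rejection.
- A paired sign test looks far superior (about 84% rejection if 20% of 40 patients are later and none earlier), but that assumes one-way discordance. With 10% earlier as well, it falls to about 13%.
- A reader might infer that this is the only formal analysis of the time-to-event endpoints. Cox models are planned in the synopsis and in Section 9.

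**Conclusion.** The sentence should be corrected, because it is unsound as written on either reading. On the literal one, the PFS test is miscalibrated towards non-significance: true size is about 1% at correlation 0.5 and about 0 at 0.8 or more, against a nominal 5%. The OS test is empty, and duration of response compares small, overlapping sets. On the responder reading, duration of response has no comparison group and PFS and OS are biased in favour of responders.

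The sizes rest on assumed survival times, censoring and correlation, none of which the documents give. The direction needs only positive within-patient correlation, which two readings of one patient's disease make very likely.

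A reader should not infer that the trial's main conclusion is at risk. The primary decision is a count of responses ("Otherwise we will enroll a maximum of 40 and reject the null hypothesis if we observe 4 or more") and does not use this test. The harm is possible false reassurance, in a secondary analysis, that the two criteria agree.

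**What to change.** In Section 9:

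1. Delete the log-rank comparison between criteria.
2. Show OS once. Show PFS and duration of response under each criterion descriptively, with 95% CIs.
3. If a comparison is wanted, make it paired: the number and percentage of patients whose irRC progression date is later than the RECIST date, the same for earlier, and the within-patient difference in restricted mean PFS with a CI from a bootstrap that resamples patients. State how irPD is dated.
4. State the limit on irRC follow-up. The synopsis schedules tumor assessments only until initial investigator-assessed progression, and Section 5.3 ends post-treatment scans at progression. Section 4.6 lets some patients continue treatment, but scans after RECIST progression are not assured. irRC PFS may therefore be informatively censored, and a paired method does not cure that.
5. If response groups were intended, say so, leave duration of response out of the test, and use a landmark or time-dependent analysis for PFS and OS.

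Cost: revised wording, slightly more analysis work and the loss of an informal p-value. None of this requires new data, but the paired comparison can be no better than the scans available after RECIST progression.

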| 
Statistical Methods:
 
For the primary endpoint of objective response rate (ORR) by RECIST v1.1 among patients with primary resistance to anti-PD-1-axis therapy, a Simon two-stage design will be employed. The design is based on our intuition for a very low anticipated response rate and not on any specific experimental evidence. The study will terminate early if there are no responses or prolonged stability (≥ 24 weeks) using irRC among the first 10 patients enrolled. Otherwise we will enroll a maximum of 40 patients with primary resistance and reject the null hypothesis of no objective response if we observe 4 or more positive responses. For a null hypothesis with a 5% ORR and alternative with a 19% ORR, this criterion has significance level 0.1 and power greater than 85%. The null and alternative hypothesis rates are not motivated by experimental evidence but rather, are examples of one pair of hypotheses that can be tested using this design.
 
Progression-free survival will be estimated with derivation of the corresponding 95% CI, plotted using the Kaplan-Meier method. Overall survival will be plotted using the Kaplan-Meier method.
 |

Time-to-event endpoints (PFS, OS) will be analyzed using the Kaplan-Meier plots. We will correlate OSS and PFS with ORR using Cox proportional hazards regression methods. No formal statistical analyses will be conducted on the 10 additional patients with acquired resistance, though the finding of immune related response in 1 or more patients would be unexpected, and should prompt further study.

Funding, Regulatory, and Feasibility Issues:

- Ipilimumab and nivolumab will be supplied by Bristol Myers Squibb Company.
- Bristol Myers Squibb Company will provide additional trial funding, including funding of serial biopsies.
- IND for trial therapy to be held by [name].

Patient Acceptability/Ethics and Consent Issues:

None anticipated

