7. CORRELATIVE/SPECIAL STUDIES

Correlative studies will be conducted on serial tumor biopsy and blood specimens. All patients will undergo a tumor biopsy prior to initiation of trial therapy, and after their 5th treatment with nivolumab (study week 10). Blood will be drawn prior to each tumor biopsy to allow additional correlative studies.

Tissue from Serial Tumor Biopsies:

- a. Multiplexed quantitative immunofluorescence will be used to evaluate multiple markers on tumor/ immune cells, including, but not limited to, PD-L1, PD-1, CK, CD4, CD8, CD20, Ki67, granzyme B, and IDO1.
- b. RNA, TCR and DNA sequencing (with neoantigen analysis)
- c. Additional studies, depending on tissue availability, may include: functional T cell studies (neoantigen stimulation assay, T cell culture) and generation of patient derived xenografts.

Serial Blood Draws:

- a. Mass cytometer (CyTOF 2, DVS Sciences) will be used to comprehensively characterize phenotypic (CD45, CD3, CD8, CD4, CD33, CD11b, CD123, CD56, CD16, CD20, CD66b, CD68, TBET, GATA-3, FOXP-3, CD14, CCR7, CD45RA, $\gamma\delta$ TCR) and functional (KI-67, HLA-DR, CD25, PD-1, CD80, CD16, IFN γ , TNF α , Granzyme B, Caspase 3, PARP) changes of blood cells in relation to changes in tumor tissue.
- b. Tetramer staining using neoantigenic peptides or ELISPOT (neoantigen stimulation assay).

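### Section 9 names Cox regression for the marker–ORR association although response is a yes/no outcome, sets no time origin for on-treatment markers, and searches for subgroups by single linkage without a cut or stability rule

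*Combined protocol and SAP*

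**What the plan says.** **Markers and outcomes.** Section 9: "Marker data and other metrics listed in Section 7 will be correlated to ORR and PFS using Cox proportional hazard regression methods". The synopsis (Statistical Methods) words the Cox analysis differently and does not mention markers: "We will correlate OSS and PFS with ORR using Cox proportional hazards regression methods".

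**Outcome definitions.** Section 8: "Objective response is defined as a complete or partial response, as determined by investigator assessment using RECIST v1.1 and irRC". Response must be confirmed, and patients who do not qualify, including those with no post-baseline scan, "will be considered non-responders in the analysis of objective response". PFS runs from the first nivolumab dose and is censored: "If a patient has not experienced progressive disease or death, PFS will be censored at the day of the last tumor assessment".

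**Timing.** The Study Calendar (Section 5.4) puts on-treatment research blood draws at W3, W5, W7 and W10, the first on-treatment imaging at W9 and the second biopsy at W10. Section 4.1.1 makes that biopsy mandatory and allows it from day 56 to day 70.

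**Subgroup search.** Section 9: "These values will be analyzed marginally using heatmaps and single linkage to identify any subpopulations". It gives no distance measure, scaling, rule for the number of clusters or stability check.

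**The concern.** Evaluating changes in tumor and blood is secondary objective E (Section 1.2), and it is what the mandatory repeat biopsy serves. Three features of the planned analysis could weaken that result.

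- Cox regression needs an event time and a censoring rule. Section 8 gives neither for response. An analyst who filled the gap with time to response would ordinarily censor early progressors, whereas Section 8 counts them as failures.
- If an on-treatment marker is entered in a PFS model that starts on day 1, some events can come before the measurement. Only patients who survived long enough to be sampled contribute, so the estimate is distorted.
- A clustering method that usually splits off one outlying patient cannot separate real groups from none.

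Whatever is left open would be settled after the data are seen, which lowers the credibility of any marker finding.

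**Working it through.** The plan gives no sample size, power or other figure for the marker analyses, so there is none to reproduce.

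**1. Outcome type.** Section 8 gives response a status for every patient and no time. PFS has a start, an event and a censoring rule. Section 9 assigns one model to both. Cox can be forced onto a yes/no outcome by giving everyone the same follow-up time, and it then becomes a relative-risk model. In one simulated set of 40 patients with 6 responders, the coefficient was 1.475 from both constant-time Cox and Poisson regression, and 2.040 from logistic regression. The plan specifies no such device, so a reader cannot tell which quantity would be reported.

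**2. Information available.** Inputs from Section 9: at most 40 patients in the primary cohort, ORR 5% or 19%, rejection at 4 or more responses.
- Expected responders: 40 × 0.05 = 2.0 and 40 × 0.19 = 7.6.
- Assume a marker split 20/20 with all k responders on one side. The smallest two-sided Fisher p is 2 × C(20,k)/C(40,k): 0.49 for k = 2, 0.11 for k = 4 and 0.003 for k = 8.

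Only small-sample methods, one marker at a time, are realistic.

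**3. Number of markers.** Section 7 names 9 immunofluorescence markers. It lists 19 + 11 = 30 cytometry markers; CD16 appears twice, leaving 29. That is 9 + 29 = 38 marker-by-specimen entries. Six names (PD-1, CD4, CD8, CD20, Ki67, granzyme B) are on both panels, so 38 − 6 = 32 distinct names. If each entry were tested once at 0.05 with no true association, 38 × 0.05 = 1.9 false positives would be expected at a time point with both tissue and blood, and 29 × 0.05 = 1.45 at a blood-only draw. These counts are illustrative, because the plan does not list its tests. It states no multiplicity control.

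**4. Order of marker and PFS event.** Counting W1 as days 1 to 7, W9 is days 57 to 63 and W10 is days 64 to 70. On the calendar the scan comes before the second biopsy and the W10 draw. Section 4.6 allows treatment beyond RECIST progression, so a patient who progresses at W9 can still give a W10 sample. Within the day 56–70 window a biopsy can also come before the scan. The W3, W5 and W7 draws precede the first scheduled scan, but they too require the patient to have reached the draw.

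**5. Single linkage.** Assumed set-up, not from the documents: 40 patients in groups of 25 and 15; 30 markers, 10 of them shifted; tree cut at two clusters; 500 runs; each marker standardised over all patients. Entries are the mean adjusted Rand index (1 = perfect recovery, 0 = chance).

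| Shift per informative marker | Single | Complete | Ward |
|---|---|---|---|
| 1.5 SD | 0.01 | 0.55 | 0.76 |
| 2 SD | 0.01 | 0.84 | 0.93 |
| 3 SD | 0.17 | 0.97 | 0.99 |

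Without that standardisation, the values at 1.5 SD are 0.01, 0.75 and 0.84, and at 3 SD single linkage reaches 0.97.

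With no true groups (zero shift, standardised), the median split was 26/14 for Ward and 29/11 for complete linkage. Single linkage isolated one patient in 98% of runs, much as it did at 1.5 SD (99%).

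**The case against.** The strongest reply is that these analyses are exploratory, that no decision rule depends on them, and that much of the plan can be run.

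- Cox for baseline markers and PFS is valid, and single linkage always returns a tree. Both points stand. A reader might infer that neither biomarker result can be obtained; the documents do not support that.
- A reader might blame single linkage's weakness on the small sample. That is wrong. In a second simulation (30/70 split, 9 markers, total separation 6 SD), the share of runs recovering the groups (adjusted Rand index above 0.8) fell from 0.46 with 40 patients to 0.00 with 200. The cause is chaining. At 8 to 10 SD and 40 patients, recovery was 0.96 to 1.00.
- Section 9 specifies no two-cluster cut, which is unfavourable to single linkage because one outlier uses up the second cluster. This stands as a limit on the simulated figures. At 3 SD a finer cut recovered most of the structure (0.84 at the best of 2 to 15 clusters); at 1.5 SD even the best cut gave only 0.18.
- Changing the linkage alone would replace one error with another, since Ward and complete linkage give fairly balanced splits from pure noise. This stands and shapes the fix.
- Section 9 does not say that week 10 markers will be modelled from day 1. True, but Section 8 gives PFS no other start, and Section 9 does not separate baseline from on-treatment markers.
- In the synopsis, response could be a covariate for survival, which Cox allows. That reading does not rescue Section 9, where markers are correlated to ORR itself. It shows that the two texts need reconciling.

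**Conclusion.** The point holds in limited form. As written, the marker–ORR analysis names a model that does not fit a yes/no endpoint, offers no alternative, and is worded differently in the synopsis. With about 2 to 8 responders in 40, under the plan's own 5% and 19% rates, the replacement must be a small-sample method applied one marker at a time.

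The PFS part of the sentence is sound for baseline markers. For on-treatment markers it lacks a time origin. Events can precede the week 10 sample, though not always, given the biopsy window.

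The clustering point is secondary. Single linkage is likely to miss moderately separated groups; how badly depends on assumed separation, scaling and cut. The documents do not support saying that subpopulations will always be missed, or that there are 38 distinct markers.

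The primary response test and the stage 1 rule are unaffected. The change is worth making because it protects a stated secondary objective at little cost.

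**What to change.** Replace the two Section 9 sentences with text to this effect, and align the synopsis so that both state whether response is the outcome or a covariate.

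- **Markers and ORR:** one marker at a time, exact or Firth logistic regression, or a rank test of responders against non-responders, with all Section 8 non-responders retained as such. Control the false discovery rate (for example Benjamini–Hochberg) across the markers tested at each time point.
- **Markers and PFS:** Cox regression from day 1 for baseline markers. For every on-treatment marker (W3, W5, W7 and week 10), start the clock at the sample date or a fixed landmark, include only patients still progression-free then, and describe earlier progressors separately.
- **Subpopulations, if clustering is kept:** Ward or complete linkage on standardised markers, with the distance, the rule for the number of clusters and a stability check (for example bootstrap) fixed in advance. The analysis should be free to conclude that there are no groups.

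The cost is SAP wording and modest programming. The on-treatment PFS models will have fewer patients and events and so less precision. No visit, sample or sample size changes.
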